6.4 STUDY INTERVENTION COMPLIANCE

Adherence to the protocol will be assessed by consistent patient presentation to all pre-described appointments including blood collection, PET-CT scans and bronchoscopies.

6.5 CONCOMITANT THERAPY

For this protocol, a prescription medication is defined as a medication that can be prescribed only by a properly authorized/licensed clinician. Medications to be reported in the medical record that include concomitant prescription medications, over-the-counter medications and supplements. After the completion of the study protocol, all study participants within the LTBI (PPD +, IGRA +) group will be recommended for referral to their local county health department or an infectious disease outpatient clinic for initiation of LTBI therapy as outlined by the WHO with the regimen selected per the recommendation of their clinician (19).

7 STUDY INTERVENTION DISCONTINUATION AND PARTICIPANT DISCONTINUATION/WITHDRAWAL

7.1 DISCONTINUATION OF STUDY INTERVENTION

Participants are free to withdraw from participation in the study at any time upon request. An investigator may discontinue or withdraw a participant from the study for the following reasons:

- In the event of a single serious adverse event (SAE) or Grade 3 or higher adverse event or laboratory abnormality that is assessed as related or possibly related to the study procedures. Events will be followed until resolution or stabilization.
- If a study participant misses one or more study appointments
- Investigator discretion
- Positive pregnancy test
- Positive COVID-19 PCR

- Current use of anticoagulant therapy including platelet inhibitors (e.g. clopidogrel), or systemic anticoagulants (e.g. warfarin, enoxaparin, or DOAC).

7.2 PARTICIPANT DISCONTINUATION/WITHDRAWAL FROM THE STUDY

Participants are free to withdraw from participation in the study at any time upon request. An investigator may discontinue or withdraw a participant from the study for the following reasons:

- Significant study intervention non-compliance
- If any clinical adverse event (AE), laboratory abnormality, or other medical condition or situation occurs such that continued participation in the study would not be in the best interest of the participant
- Subject has completed the study follow-up period
- Death
- Screen Failure

The reason for participant discontinuation or withdrawal from the study will be recorded on the Case Report Form (CRF). Subjects who sign the informed consent form and are assigned to a cohort but do not receive the study intervention may be replaced. Subjects who sign the informed consent form and subsequently withdraw, or are withdrawn or discontinued from the study, will be replaced.

7.3 LOST TO FOLLOW-UP

A participant will be considered lost to follow-up if he or she fails to return for one scheduled visit and is unable to be contacted by the study site staff.

The following actions must be taken if a participant fails to return to the clinic for a required study visit:

- The site will attempt to contact the participant and reschedule the missed visit within three days and counsel the participant on the importance of maintaining the assigned visit schedule and ascertain if the participant wishes to and/or should continue in the study.
- Before a participant is deemed lost to follow-up, the investigator or designee will make every effort to regain contact with the participant (where possible, 3 telephone calls and, if necessary, a certified letter to the participant's last known mailing address or local equivalent methods). These contact attempts should be documented in the participant's medical record or study file.
- Should the participant continue to be unreachable, he or she will be considered to have withdrawn from the study with a primary reason of lost to follow-up.

8 STUDY ASSESSMENTS AND PROCEDURES

8.1 SCREENING PROCEDURES

Screening activities performed prior to obtaining informed consent

Minimal risk activities that may be performed before the subject has signed a consent include the following:

- Email, written, in person or telephone communications with prospective subjects
- Review of existing medical records to include H&P, laboratory studies, etc.

Once the research team has identified a potential subject for the study, the subject will be asked to come to the NIH. The study team will consent the subject via in person, telephone and or Telehealth visit platform, allowing time for the subjects to ask questions and make a voluntary decision.

The following tests will be performed to determine eligibility.

- Review of medical history including history of Mtb Exposure
 - History of exposure to persons with active TB
 - History of residence in a TB-endemic country
 - Estimate of time when LTBI most likely occurred
 - Exposure to Bacillus Calmette–Guérin (BCG) vaccine
- Review of concurrent medications and vaccinations performed within the last year
 - Of note, eligibility review and procedures will be completed at least 2 weeks following most recent vaccination

The following tests will be performed after informed consent is obtained to determine eligibility.

- Vital signs
- Complete blood count with diff, acute care panel, hepatic care panel, LDH, International Normalized Ratio (INR), Prothrombin Time (PT), and Partial Thromboplastin Time (PTT) , interferon gamma release assay (IGRA), HIV (I/II), Hepatitis B and C
- Plasma or urinary HCG in female subjects who are of child-bearing age will be collected (after informed consent and within 7 days of any research study procedure)
- Tuberculin skin test (TST) will be performed and read within 48 to 72 hours. A second TST (two-step) may be performed on individuals who have a positive IGRA result, but negative TST result on initial screening. Two-step TST will be performed 1 to 3 weeks after the 1st test.
- Chest X-Ray
- EKG
- COVID-19 PCR

8.2 EFFICACY ASSESSMENTS

8.2.1 Clinical Evaluations

Physical examination

History and physical examination with vital signs (weight, height, BMI, blood pressure, respirations, heart rate, temperature and oxygen saturation) will be performed at screening with focus on respiratory and cardiovascular systems. Repeat physical examinations with focus on respiratory and cardiovascular systems with vital sign measurements (blood pressure, respirations, heart rate, temperature and oxygen saturation) will be performed prior to each bronchoscopy.

Radiographic or other imaging assessments.

Chest PET-CT Scan

Subjects will undergo a total of 3 PET/CT scans. A baseline PET/CT of the chest will be performed no more than one week prior to the initial bronchoscopy (10). In order to examine early immune responses, on day 4 post instillation bronchoscopy, a second PET-CT scan will be obtained. Furthermore, in order to examine the persistence of immune cell metabolic activity in the pulmonary parenchyma and thoracic lymph nodes, a PET-CT image will be obtained on approximately day 20 post initial bronchoscopic challenge.

Each participant will be asked to provide an estimate of their radiation exposure within the calendar in order to assess if participation in the study will cause a participant to exceed his/her annual dose limit.

8.2.2 Biospecimen Evaluations

Biological specimen collection and laboratory evaluations.

A peripheral intravenous catheter will be placed to obtain blood for analysis (up to 120 mL). The whole blood volume will be divided into aliquots for myeloid cell flow cytometry analysis, peripheral blood mononuclear cell (PBMC) isolation and laboratory testing. PBMC isolation and subsequent in-vitro stimulation with PPD antigen is detailed below. Blood for clinical serologic testing will be sent to the NIH chemistry lab for analysis via complete metabolic panel (CMP) and c-reactive protein (CRP) and the hematology lab for analysis via complete blood count with differential count (CBC w/ diff) and erythrocyte sediment count (ESR). The amount of blood that may be drawn from adult patients and volunteers (i.e., those persons 18 years of age or older) for research purposes shall not exceed 10.5 mL/kg or 550 mL, whichever is smaller, over any eight-week period.

In order to assess for any concurrent lower respiratory tract infection in study subjects, a 2 mL aliquot of bronchoalveolar lavage (BAL) fluid from day 0, day 5 and day 21 will be set aside from the research analysis sample. This BAL aliquot will be sent to the NIH Clinical Center Microbiology department for bacterial gram stain and culture in addition to BioFire respiratory pathogen panel for detection of the following viral and bacterial organisms: Adenovirus, Coronavirus HKU1/NL63/229E/OC43, Human Metapneumovirus, Human Rhinovirus/Enterovirus, Influenza A, Influenza B, Parainfluenza, Respiratory Syncytial Virus, Bordetella pertussis, Chlamydia pneumoniae, and Mycoplasma pneumoniae.

8.2.3 Correlative Studies for Research/Pharmacokinetic Studies

Special assays or procedures required

Blood will be collected into heparinized Green Top tubes on the day of each bronchoscopy (days 0, 5 and 21). Peripheral Blood Mononuclear Cell (PBMC) and BAL cells will be isolated, stimulated and cell surface molecules, intracellular cytokines and transcription factors will be evaluated via flow cytometry. Peripheral blood and BAL soluble mediators will be analyzed via multiplex kits, mass spectrometry or other techniques.

8.2.4 Samples for Genetic/Genomic Analysis

Not applicable.

8.3 SAFETY AND OTHER ASSESSMENTS

First participants will undergo history and physical assessment, blood or urine pregnancy test and a confirmatory TB skin test, and have blood drawn for an interferon gamma release assay (IGRA; Quantiferon Gold In-Tube, Qiagen) screening. Subjects will undergo a chest x-ray (CXR) to rule out for active disease. This is to ensure their eligibility prior to undergoing PET/CT scans, and bronchoscopies.

Eligible study subjects will be given a username and password to access a web-based patient self-reporting diary to record any evidence of self-assessed adverse events. At each study visit this will be reviewed with the subject by a designated research study personnel. If a subject reports a possible serious adverse event, then the subject will be contacted immediately for review of event(s) by designated research study personnel. Subjects will also be directed to contact research study nurse if they have any concerns or questions.

Biological specimen collection and laboratory evaluations.

Bronchoscopy, BAL and Bronchoscopic Instillation

Study subjects will undergo three bronchoscopies and bronchoalveolar lavages for the evaluation of airway and alveolar immune cells.

The study subject will be required to be without solid food or drink after midnight or six hours prior to each bronchoscopy.

First, topical anesthesia will be achieved via administration of inhaled medications containing lidocaine. Following completion of local anesthesia, sedative medications will be administered to achieve a level of moderate sedation.

A bronchoscope will be introduced via the trans-oral or trans-nasal route. Lidocaine will be instilled through the bronchoscope at the levels of the epiglottis, vocal cords, carina and mainstem bronchi to provide additional anesthesia during the procedure. A baseline (prior to control or PPD instillation) bronchoalveolar lavage (BAL) will be performed in the left superior lingular segment of the left upper lobe. The control instillation of normal saline will then be placed into the anterior segment of the left upper lobe. This instillation will be performed via introduction of a balloon-tipped 5-French pulmonary artery (PA) catheter (26). Next, the bronchoscope will be moved to the right lung, similarly, a baseline BAL will be performed in the right middle lobe medial segment. Immediately afterwards, tuberculin purified protein derivative will be instilled into the anterior segment of the right upper lobe via a separate 5-French balloon-tipped PA catheter. The bronchoscope will then be removed and the subject will recover and be monitored. If a subject requires additional monitoring they will be transferred to the Day Unit of the Clinical Center. Signs and symptoms for expected and unexpected responses from bronchoscopy and PPD instillation will be assessed during this time. At time of discharge their vital signs must return to baseline, the subject must be able to eat and drink without difficulty and have a responsible adult available for transport from the Clinical Center. Each participant will be called the following day to assess their respiratory status and evaluate for the development of any new pulmonary symptoms. If necessary, they will be re-evaluated at the Clinical Center by [name].

Provide Study Monitoring Plan:

We will use the Common Terminology Criteria for Adverse Events for Adverse Events (CTCAE) Version 5.0 to assess for any adverse events related to endobronchial PPD instillation. Adverse events (AE) will be graded by their level of severity (Grade 1 mild, Grade 2 moderate, Grade 3 severe, Grade 4 life-threatening consequences, Grade 5 Death related to AE). We will specifically assess for evidence of respiratory-related adverse events commonly associated with bronchoscopy and/or endobronchial administration of a non-endogenous agent which includes but is not limited to: dyspnea, cough, sore throat, stridor, wheezing, bronchospasm, hypoxia, laryngeal inflammation, laryngospasm, pneumonitis, or pneumothorax. We will similarly assess for evidence of systemic immune- or infectious-related adverse events including but not limited to: allergic reaction, anaphylaxis, bronchial infection, lung infection, pharyngitis and/or pleural infection.

8.4 ADVERSE EVENTS AND SERIOUS ADVERSE EVENTS

8.4.1 Definition of Adverse Event

Any untoward medical occurrence in a human subject, including any abnormal sign (e.g., abnormal physical exam or laboratory finding), symptom, or disease, temporally associated with the subject's participation in the research, whether or not considered related to the subject's participation in the research (21 CFR 312.32 (a)).

8.4.2 Definition of Serious Adverse Events (SAE)

An adverse event (AE) or suspected adverse reaction is considered "serious" if, in the view of either the investigator or sponsor, it results in any of the following outcomes: death, a life-threatening adverse event, inpatient hospitalization or prolongation of existing hospitalization, a persistent or significant incapacity or substantial disruption of the ability to conduct normal life functions, or a congenital anomaly/birth defect. Important medical events that may not result in death, be life-threatening, or require hospitalization may be considered serious when, based upon appropriate medical judgment, they may jeopardize the participant and may require medical or surgical intervention to prevent one of the outcomes listed in this definition. Examples of such medical events include allergic bronchospasm requiring intensive treatment in an emergency room or at home, blood dyscrasias or convulsions that do not result in inpatient hospitalization, or the development of drug dependency or drug abuse.

8.4.3 Classification of an Adverse Event

8.4.3.1 Severity of Event

This study will utilize the Common Terminology Criteria for Adverse Events version 5.0 (CTCAE v5.0) for toxicity and adverse event reporting. A copy of the CTCAE v5.0 can be downloaded from the https://ctep.cancer.gov/protocolDevelopment/electronic_applications/ctc.htm.

AEs will be recorded, verified, and followed until satisfactory resolution or stabilization. Severity definitions found in the CTCAE v5.0 will be used for grading the severity (intensity) of AEs:

- **Mild** – Events require minimal or no treatment and do not interfere with the participant's daily activities.
- **Moderate** – Events result in a low level of inconvenience or concern with the therapeutic measures. Moderate events may cause some interference with functioning.

- **Severe** – Events interrupt a participant’s usual daily activity and may require systemic drug therapy or other treatment. Severe events are usually potentially life-threatening or incapacitating. Of note, the term “severe” does not necessarily equate to “serious”.
- **Life-threatening** – Events with life-threatening consequences in which urgent intervention is indicated
- **Death** – Death related to an adverse event

8.4.3.2 Relationship to Study Intervention

All adverse events (AEs) must have their relationship to study intervention assessed by the investigator who examines and evaluates the participant based on temporal relationship and his/her clinical judgment. The degree of certainty about causality will be graded using the categories below. In a clinical trial, the study product must always be suspect.

- **Related** – The AE is known to occur with the study intervention, there is a reasonable possibility that the study intervention caused the AE, or there is a temporal relationship between the study intervention and event. Reasonable possibility means that there is evidence to suggest a causal relationship between the study intervention and the AE.
- **Not Related** – There is not a reasonable possibility that the administration of the study intervention caused the event, there is no temporal relationship between the study intervention and event onset, or an alternate etiology has been established.

8.4.3.3 Expectedness

The principal investigator will be responsible for determining whether an adverse event (AE) is expected or unexpected. An AE will be considered unexpected if the nature, severity, or frequency of the event is not consistent with the risk information previously described for the study intervention. The expected risks will be primarily related to bronchoscopy and endobronchial manipulations. These risks include: dyspnea, cough, sore throat, stridor, wheezing, bronchospasm, hypoxia, laryngeal inflammation, laryngospasm, pneumonitis, pneumothorax, allergic reaction, and anaphylaxis. We expect some vasovagal symptoms during blood draws (expected frequency 50%) and transient bruising at the site of blood draws (expected frequency 50%).

8.4.4 Time Period and Frequency for Event Assessment and Follow-Up

The occurrence of an adverse event (AE) or serious adverse event (SAE) may come to the attention of study personnel during study visits and interviews of a study participant presenting for medical care, or upon review by a study monitor.

All AEs including clinically significant laboratory tests, local and systemic reactions not meeting the criteria for SAEs will be captured on the appropriate case report form (CRF). Information to be collected includes event description, time of onset, clinician’s assessment of severity, relationship to study product/research procedure (assessed only by those with the training and authority to make a diagnosis), and time of resolution/stabilization of the event. All AEs occurring while on study must be documented appropriately regardless of relationship. All AEs will be followed to adequate resolution.

Any medical condition that is present at the time that the participant is screened will be considered as baseline and not reported as an AE. However, if the study participant's condition deteriorates at any time during the study, it will be recorded as an AE.

Changes in the severity of an AE will be documented to allow an assessment of the duration of the event at each level of severity to be performed. AEs characterized as intermittent require documentation of onset and duration of each episode.

The principal investigator will record all reportable events with start dates occurring any time after informed consent is obtained until 7 (for non-serious AEs) or 30 days (for SAEs) after the last day of study research procedure or until resolution or stabilization of an SAE whichever comes later. At each study visit, the investigator will inquire about the occurrence of AE/SAEs since the last visit. Events will be followed for outcome information until resolution or stabilization via in person, telephone and or e-mail.

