1.3 SCHEDULE OF ACTIVITIES (SOA)

Schedule of Activities (SOA) AND ASSESSMENTS	EVALUATION	Screen*	Baseline						Study Visits 3 to 6			Telephone Follow- up Day 30
PROTOCOL TIMEPOINT			V1	V2	V3	V4**		V5	V6**			
Window +/- days	-60 Days	-7 Days			-2 /+3 D				-5 /+6D			
day /month				D0	D4	D5	D20	D21				
Assessments												
Review Inclusion/Exclusion Criteria	X											
Consent to study	X											
Review Medical History with Mtb Exposure		X ¹										
Review of Medications	X	X	X	X	X	X	X	X	X			
Physical Examination	X	X	X	X	X	X	X	X	X			
Weight, Height, and BMI	X											
Vital Signs (BP, HR, Resp, Temp O ₂ Saturation)	X	X	X			X			X			
Adverse Event Review			X	X	X	X	X	X	X		X	
CHEMISTRY LABS												
Female, Pregnancy Test (blood or urine) ²	X	X	X	X	X	X	X	X	X			
Acute Care Panel	X	X		X					X			
Mineral Panel	X	X		X				X			X	
CRP	X	X		X			X		X			
Hepatic Panel	X	X			X			X				
LDH	X	X		X			X		X			
International Normalized Ratio (INR), Prothrombin Time (PT), and Partial Thromboplastin Time PTT		X ³	X ³		X ³			X ³				
COVID-19 (PCR)	X											
HEMATOLOGY LABS												
CBC with differential	X	X		X			X		X			
ESR	X	X		X			X		X			
Viral Serologies												
Hepatitis B, C	X											
HIV	X											
Additional Tests												
*QuantiFERON Gold Test (IGRA)	X									X		
*Tuberculin skin test (TST)	X ⁴											
EVALUATIONS												
EKG	X		X		X			X		X		
*Chest X-RAY	X											
Chest PET-CT			X		X			X				
PROCEDURES												
Bronchoscopy					X ³			X ³		X ³		

STUDY MEDICATION							
Installation of Tuberculin Purified Protein Derivative (PPD) and saline			X				
Removal of Tuberculin Purified Protein Derivative (PPD) and saline cells				X		X	
Research Samples							
Immunology Assays = 40 mL via heparinized green top tubes			X	X		X	

* = Medical history screening activities may be done utilizing the Telehealth Visit Platform. Screening tests may be used as baseline if performed within 60 days. If re-screened after 60 days, the TST, IGRA, & chest x-ray will not be repeated unless there is a known tuberculosis exposure, including but not limited to travel to an endemic area or direct contact with an individual with known or suspected tuberculosis disease.

x¹ = History of exposure to persons with active TB; History of residence in a TB-endemic country and Estimate of time when LTBI most likely occurred

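### Section 8.4.4 ends recording of new non-serious AEs 7 days after the last procedure, so an instilled participant who leaves after day 0 or day 5 is covered only to day 7 or day 12 after PPD, against day 28 for a completer

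*Combined protocol and SAP*

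**What the plan says.** Section 8.4.4 records events that start after consent and "until 7 (for non-serious AEs) or 30 days (for SAEs) after the last day of study research procedure", with the extension "or until resolution or stabilization of an SAE whichever comes later". The extension is for SAEs only. The same section makes routine inquiry visit-based: "At each study visit, the investigator will inquire about the occurrence of AE/SAEs since the last visit".

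PPD is given once, at the first bronchoscopy (section 8.3). Section 8.2.3 puts the bronchoscopies on days 0, 5 and 21.

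For participants who stop, section 7.1 says of a related SAE or Grade 3 or higher event: "Events will be followed until resolution or stabilization". Section 7.2 has the reason for leaving entered on the CRF and the participant replaced. Section 7.3 provides for attempts to reach someone who misses a visit. The schedule in section 1.3 has a row "Adverse Event Review" and a telephone follow-up on day 30, where the last mark in that row appears to fall. None of these places says whether the day 30 call is made to someone who has withdrawn.

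**The concern.** The only exposure that is specific to this trial is the PPD instillation, yet the end of recording is counted from whichever research procedure came last. Time under observation after PPD therefore depends on how long the participant stays. Someone who leaves early has the shortest period in which a new non-serious event would be recorded, and visit-based inquiry stops when the visits stop.

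What is at stake is small but concrete. Section 10.2 lists, as circumstances that may warrant suspension, the same or similar Grade 3 or higher AE in 2 or more subjects and a Grade 3 or higher laboratory abnormality in 3 or more. A Grade 3 event that is not an SAE falls under the 7-day rule. With thresholds of 2 and 3 subjects, one unrecorded event can decide whether a count is reached. Nothing later in the plan would show the shortfall: section 9.3.1 (evaluable for toxicity) and section 9.4.3 (safety analyses) are both marked not applicable.

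**Working it through.** **Inputs**
- PPD instillation: day 0 (sections 1.3 and 8.3).
- Procedure days: bronchoscopy on days 0, 5 and 21 (section 8.2.3); PET-CT on days 4 and 20 (section 1.3).
- Visit windows: −2/+3 days for the early visits and −5/+6 days for the late visits (section 1.3, as far as the table can be read).
- Recording rule: last procedure + 7 days for non-serious AEs, + 30 days for SAEs (section 8.4.4).

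**Assumption.** Section 8.4.4 does not define the research procedure that it counts from. I read it as the participant's own last one.

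**Formula.** With p the day of the last procedure, non-serious recording ends on day p + 7 and SAE recording on day p + 30. The plan gives only this rule and no end day counted from PPD, so there is no stated figure to reproduce.

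| Last procedure | p | Non-serious AEs end, p + 7 (with visit windows) | SAEs end, p + 30 (with visit windows) |
|---|---|---|---|
| Visit 2, PPD | 0 | 7 | 30 |
| Visit 3, PET-CT | 4 | 11 (9 to 14) | 34 (32 to 37) |
| Visit 4, bronchoscopy | 5 | 12 (10 to 15) | 35 (33 to 38) |
| Visit 5, PET-CT | 20 | 27 (22 to 33) | 50 (45 to 56) |
| Visit 6, completer | 21 | 28 (23 to 34) | 51 (46 to 57) |

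**Shortfall for non-serious AEs at nominal timing**
- Leaves after day 0: 28 − 7 = 21 days fewer after PPD, 21/28 = 75% of the completer's period.
- Leaves after day 5: 28 − 12 = 16 days fewer, 16/28 = 57%.

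**Would the day 30 call close the gap by itself?** Take a new non-serious event that starts on day 10. In a completer, 10 ≤ 28, so it is recorded. In someone whose last procedure was on day 0, 10 > 7, so it lies outside the rule even if the participant is telephoned on day 30. The recording rule and the call both need changing.

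**How many people.** Section 9.2 allows up to 5 extra participants to obtain 20 completed studies: 5/25 = 20%. This is a ceiling, because section 7.2 also replaces people who were never instilled.

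**A neighbouring mismatch.** A completer's SAE window runs to day 51. The stated participant duration is 30 days (section 1.1) and the last scheduled contact is on day 30, so 51 − 30 = 21 days of SAE recording have no scheduled contact. The day 30 call also falls 30 − 28 = 2 days after a completer's non-serious window has closed.

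**The case against.** The case for leaving the rule alone has real content.

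- **Anchoring to the last procedure is defensible.** Section 8.4.3.3 attributes the expected risks mainly to bronchoscopy, and everyone gets the same 7 days after the last one. A completer's longer period partly covers two further bronchoscopies that a leaver never had, so the 75% and 57% are not a pure loss of like-for-like observation. This stands. What remains is that observation after PPD itself is unequal.
- **There is other cover.** Participants are called the day after the bronchoscopy, keep a web diary, are contacted at once if they report a possible SAE, and are told to ring the research nurse with concerns (section 8.3). Section 8.4.4 follows known AEs to resolution. Section 7.3 gives up to three calls and a letter. These narrow the gap. But the day-after call comes too early, the diary is reviewed at visits, and the section 7.3 attempts aim to regain contact with people who have missed a visit. None is a stated inquiry about new events after withdrawal.
- **Day 7 is the extreme case.** It applies only when nothing is done after day 0. The schedule table is broken in the text available, so the lack of an early-termination column is weak evidence. Both points are fair. The finding rests on the wording of 8.4.4 and of 7.1 to 7.3.
- **The requirement to document all AEs while on study** (section 8.4.4) might be thought to override the window. It does not help someone who has left the study. For a completer it could extend recording to day 30 and so widen the difference.

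A reader might go further and infer that leavers are the people who reacted. The documents do not support that: section 7.1 also lists missed visits, pregnancy, a positive COVID-19 PCR and anticoagulant use. Section 7.1 makes withdrawal after a reaction possible, and no more than that.

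**Conclusion.** The point holds for new non-serious AEs, including non-serious Grade 3 events. At nominal timing, and reading the rule as the participant's own last procedure, an instilled participant who leaves after day 0 or day 5 is covered to day 7 or day 12 after PPD, against day 28 for a completer (day 23 to 34 within the visit windows). No section says that the day 30 call applies after withdrawal. The number affected is at most about 5 of 25.

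Three stronger readings are not supported:
- **A serious loss of SAE data.** The earliest leaver still has SAEs recorded to day 30 after PPD, which equals the whole stated participant duration. Completers have no scheduled contact after day 30 either.
- **Biased comparison of AE rates between groups.** Section 10.2 uses absolute counts, no safety analysis is planned, and section 10.5 says only that the DSMB reviews safety data on each arm. A missed event can lower a count, but no planned comparison of rates is distorted.
- **Late harm expected because PPD activity lasts to day 21.** The protocol studies persistence, but sections 4.1 and 9.1 hypothesise an early peak followed by waning.

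**What to change.** 1. In section 8.4.4, for everyone who receives PPD, record all AEs until the later of the current window and the day 30 telephone follow-up, counted from instillation. For non-serious AEs the end becomes the later of p + 7 and 30. That moves a day 0 leaver from day 7 to day 30, a day 5 leaver from day 12 to day 30, and an on-schedule completer from day 28 to day 30. A completer whose last visit falls on day 27 keeps day 34. No current window is shortened.
2. In section 7.2 and the schedule, state that the day 30 telephone AE review is done for every instilled participant, including those withdrawn, unless they refuse contact.
3. In section 8.4.4, define which procedures count as research procedures and say that the last one is the participant's own.
4. Reconcile the completer's SAE window (to about day 51) with the 30-day participant duration in section 1.1 and the last scheduled contact on day 30.

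The cost is a wording amendment and one or two calls for each early leaver, at most about 5 people. Some will decline contact, and for them the gap stays. It adds no visit or procedure.
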